Title

Conservative versus Interventional Management of Postsurgical CSF
Pseudomeningocele: A Randomized Controlled Trial

NCT number

Not yet assigned

Unique protocol ID

108/20-55/2025

Date

22th May 2026

1. Background and Rationale

Background:

Postsurgical pseudomeningocele formation is a relatively common complication after intracranial surgery, often associated with fluid collection at the surgical site. Management approaches vary, with options including conservative treatment or interventional strategies such as revision surgery, insertion of lumbar drainage, or simple wound puncture. Current evidence on the most effective treatment is limited, and there is a need for randomized controlled trials to evaluate the outcomes of these approaches.

Rationale:

This trial aims to determine whether an interventional approach offers superior outcomes compared to conservative management in terms of pseudomeningocele absorption and overall patient recovery.

2. Objectives and Hypotheses

Primary Objective:

1. New onset of wound CSF leakage necessitating revision surgery

Secondary Objectives:

1. To compare the infection rate between the two treatment groups.
2. To assess functional recovery using the Glasgow Outcome Scale–Extended (GOSE) at 1 year post-surgery.
3. Absorption of pseudomeningocele at 4 months and 1 year post-surgery assessed by CT or MRI
4. Persistence of headache after the surgery – Pain Scale 0-10 (VAS)

Null Hypothesis:

There is no significant difference in the rate of CSF leakage and pseudomeningocele absorption at 4 months and 1 year, as measured by CT or MRI, between patients treated with conservative management and those undergoing interventional procedures (revision surgery, lumbar drainage, or simple puncture). Additionally, there is no significant difference in secondary outcomes, such as infection rates and functional recovery (measured by the Glasgow Outcome Scale–Extended), between the two groups.

3. Study Design

This study is a **parallel-group, randomized controlled trial** with two arms:

- **Interventional Group:** Patients undergoing local treatment - lumbar drainage insertion, simple wound puncture, fibrin glue or any combination.
- **Conservative Group:** Patients managed without surgical procedures, except for skin sutures.

Patients will be followed for a total of 1 year with CT or MRI assessments at 4 months and 1 year post-surgery.

4. Participants / Population

Inclusion Criteria:

- Patients aged 18-80 years who have developed a pseudomeningocele following elective intracranial surgery.
- Diagnosed fluctuation during clinical examination after the surgery, Pseudomeningocele Palpation Scale (PPS), II-IV

I No or minimal fluctuation; underlying bone is clearly palpable with light palpation.

II Definite fluctuation; underlying bone or muscle is palpable with moderate pressure.

III Marked fluctuation; underlying structures are palpable only with firm pressure.

IV Tense lesion; painful and/or erythematous; underlying structures are not palpable even with firm pressure.

Light palpation: minimal pressure without causing discomfort

Moderate pressure: increased pressure causing awareness but no pain

Firm pressure: strong pressure causing discomfort or mild pain

- Willing and able to give informed consent.
- No prior history of previous cranial or spinal surgical intervention.

Exclusion Criteria:

- Patients with pseudomeningocele due to emergency or trauma-related surgeries.
- Known or suspected infection at the pseudomeningocele site at the time of recruitment.
- Severe comorbid conditions preventing participation (e.g., terminal illness, severe organ failure).
- Patients with conditions that require urgent surgical intervention not related to pseudomeningocele management.

5. Interventions

Interventional Arm:

- Patients will undergo one of the following procedures based on clinical judgment:
 1. **Revision surgery:** Surgical intervention to drain the pseudomeningocele and ensure proper wound closure.
 2. **Lumbar drainage insertion:** Placement of a lumbar drain to facilitate cerebrospinal fluid (CSF) diversion.
 3. **Simple puncture:** Needle aspiration of the pseudomeningocele under sterile conditions.

Conservative Arm:

- Patients will receive conservative management, with no surgical procedures other than the application of skin sutures if required. Monitoring and wound care will be provided.
-

6. Outcomes

Primary Outcome:

- **New onset of wound CSF leakage or tension pseudomeningocele necessitating revision surgery**

Secondary Outcomes:

- **Infection rate:**
Incidence of infection related to the pseudomeningocele or any interventions, including signs of local infection, meningitis, or systemic sepsis, within 1 year.
 - **Functional recovery (GOSE):**
The Glasgow Outcome Scale–Extended (GOSE) will be assessed at 1 year post-surgery to evaluate functional outcomes and quality of life. GOSE scores range from 1 (death) to 8 (upper good recovery).
 - **Pseudomeningocele absorption on CT or MRI:**
The primary outcome is the resolution or reduction of the pseudomeningocele, assessed through CT or MRI at **4 months** and **1 year** post-surgery. Scans will be reviewed by blinded radiologists, and pseudomeningocele size will be measured and recorded.
 - **Visual Analogue Scale**
-

7. Randomization and Blinding

Randomization:

Participants will be randomized in a 1:1 ratio to the interventional or conservative treatment arms using a computer-generated randomization sequence. Randomization will be stratified by age and body mass index.

Blinding:

Due to the nature of the interventions, patients and surgical teams cannot be blinded to group allocation. However, the radiologists interpreting the CT or MRIs and the independent data assessors evaluating outcomes will be blinded to the treatment arm.

8. Sample Size Calculation

A sample size of **60 patients** (30 per group) will be required to detect a clinically significant difference in pseudomeningocele absorption between the two groups, with a power of 80% and an alpha of 0.05.

9. Statistical Analysis

- **Primary outcome:**
The proportion of patients requiring revision surgery for CSF leakage or tension pseudomeningocele at 4 months and 1 year will be compared between the two groups using a chi-square test. Time-to-absorption analyses will be conducted using Kaplan-Meier survival curves and log-rank tests.
 - **Secondary outcomes:**
Infection rates will be compared using Fisher's exact test, and GOSE scores will be analyzed using a Mann-Whitney U test to assess differences in functional recovery between groups.
 - **Multivariate analysis:**
Multivariate logistic regression will be used to adjust for potential confounders, such as baseline health status, age, and type of initial surgery.
-

10. Ethical Considerations

The study will be conducted following the principles of the Declaration of Helsinki. Informed consent will be obtained from all participants before enrollment. The study protocol has been approved by the institutional review board (IRB). The risks associated with interventional approaches (e.g., infection, procedural complications) will be disclosed to patients during the consent process.

11. Follow-up and Monitoring

Participants will be followed for a total of 1 year. Follow-up visits will include clinical assessments at **4 months** and **1 year**, as well as CT or MRI scans at these time points. Infection surveillance will occur throughout the study, and any adverse events will be recorded and reported to the IRB.

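### The 4-month absorption scan is timed from the index operation, not from randomisation, with no cap on the gap between them, so exposure to the allocated strategy at that scan is uncontrolled and the 4-month contrast is diluted

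*Protocol*

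**What the plan says.** The absorption scans are tied to the operation in three places. Section 2 lists "Absorption of pseudomeningocele at 4 months and 1 year post-surgery assessed by CT or MRI" as an objective, Section 3 schedules "CT or MRI assessments at 4 months and 1 year post-surgery", and Section 6 repeats the two time points on the same clock. GOSE follows the same origin: in Section 6 it "will be assessed at 1 year post-surgery to evaluate functional outcomes and quality of life".

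Entry comes later than that origin. Section 4 admits patients "who have developed a pseudomeningocele following elective intracranial surgery", with the clinical sign defined as "Diagnosed fluctuation during clinical examination after the surgery". Neither criterion limits how long ago the operation may have been.

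Section 7 does not say when randomisation takes place relative to surgery or diagnosis, and the interval is not a stratification factor: "Randomization will be stratified by age and body mass index". Section 11 repeats the 4-month and 1-year visits without an origin. Section 9 plans Kaplan-Meier curves for time to absorption without a time zero. No section times any outcome from randomisation.

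**The concern.** A randomised comparison measures what the allocated strategy does after allocation. Here the clock starts at an event that precedes allocation by an unknown and variable time. A patient enrolled 3 months after the operation has the 4-month scan 1 month after randomisation. A patient enrolled after 4 months has already passed that time point, and nothing in Section 4 keeps such a patient out.

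What is at stake is the sensitivity of the 4-month absorption comparison. Section 8 justifies the sample size by a difference in absorption, without saying at which of the two time points. Visit timing and entry criteria are fixed by the protocol. An analysis plan cannot move a scan already taken or add an entry window afterwards, so this is not a detail that can wait.

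**Working it through.** **The plan's own figure.** Section 8 gives 30 per group, 80% power and alpha 0.05, but no absorption rates and no difference, so 60 cannot be reproduced. Solving backwards (two-sided 5%, pooled-variance formula, no continuity correction), 30 per arm detects about 30% vs 65.5%, 40% vs 75% or 50% vs 83.5%. The illustrations below use pairs close to that range.

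**Assumptions (none is in the protocol).**
- Absorption occurs at a constant rate λ in each arm, counted from randomisation. λ is set so that the stated proportion is absorbed after 4 months of allocated treatment: λ = −ln(1 − p)/4.
- The delay from operation to randomisation is uniform over 0 to d months, with the same distribution in both arms.
- There are 30 patients per arm and the test is two-sided at 5%.

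**Formulas.** The expected proportion absorbed at a scan T months after surgery, averaged over the delay, is

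p(T, d) = 1 − e^(−λT) × (e^(λd) − 1)/(λd).

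Power = Φ[(|p2 − p1| − 1.96 × se0)/se1], where se0 = √(2 p̄(1 − p̄)/30), se1 = √([p1(1 − p1) + p2(1 − p2)]/30), and p̄ is the mean of p1 and p2.

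**One case in full: 33% vs 67%, T = 4, d = 3.**
- λ1 = −ln(0.67)/4 = 0.1001; λ2 = −ln(0.33)/4 = 0.2772.
- p1 = 1 − 0.67 × (e^0.3004 − 1)/0.3004 = 0.218.
- p2 = 1 − 0.33 × (e^0.8315 − 1)/0.8315 = 0.485.
- The difference is 26.7 points; se0 = 0.1233; se1 = 0.1184.
- Power = Φ[(0.267 − 0.2417)/0.1184] = Φ(0.21) = 58%.

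**4-month scan.**

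| Delay (months) | 33% vs 67%: difference, power | 50% vs 83%: difference, power |
|---|---|---|
| none | 34.0 points, 76% | 33.0 points, 79% |
| 0-0.5 | 33.3 points, 74.5% | 33.2 points, 78% |
| 0-1 | 32.4 points, 72% | 33.2 points, 77% |
| 0-2 | 30.1 points, 67% | 32.4 points, 73% |
| 0-3 | 26.7 points, 58% | 30.0 points, 65% |

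In the second pair, short delays leave the raw difference unchanged. The small loss of power arises because the proportions move towards the middle of the scale, where the variance is larger.

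**1-year scan, same model.** With delays of 0-3 months, the difference for the first pair goes from 26.5 to 29.5 points and power from 80% to 83%. For the second pair the difference goes from 12.0 to 15.4 points and power from 47% to 56%. The reason is that the slower arm is catching up by then, so slightly less exposure leaves the arms further apart. The model gives no loss at 1 year.

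**The case against.** The strongest reply is that the effect is confined to one time point and depends on delays nobody has seen. That largely stands. The 1-year scan loses nothing under the model used, and GOSE is measured only at 1 year, so no harm to it is shown. If enrolment follows surgery within about two weeks, the 4-month loss is 1-2 points. Scans falling before randomisation require enrolment beyond 4 months; the protocol permits this, but nothing shows it is expected.

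A reader might go further in three ways that the documents do not support.

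- **Bias between arms from the delay itself.** Allocation is random, so delays are balanced in expectation. They blunt the 4-month contrast but do not tilt it.
- **A clock that restarts in one arm.** Section 5 lists revision surgery among the interventional options ("Surgical intervention to drain the pseudomeningocele and ensure proper wound closure"), so one might fear that those patients would be timed from the revision. But the protocol consistently calls that operation revision surgery, and in Section 4 unqualified surgery can only mean the operation that preceded the diagnosis. A restart is not a fair reading.
- **Harm to the revision-surgery outcome.** Section 9 analyses "The proportion of patients requiring revision surgery for CSF leakage or tension pseudomeningocele at 4 months and 1 year" but states no origin for those times. No wrong clock is fixed there, and an analysis plan may settle it.

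What remains is the 4-month absorption scan, where the protocol does fix an origin before allocation and sets no entry window.

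**Conclusion.** The point holds for the 4-month absorption scan. As written, a patient can follow the protocol exactly and have that scan shortly after randomisation, or reach its due date before randomisation.

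Under assumed constant absorption rates and delays spread evenly over up to 3 months, power falls by as much as 18 points (76% to 58%) in one scenario and 14 points (79% to 65%) in the other. With delays of up to 1 month the loss is about 2-4 points. These figures illustrate scale only, since the protocol gives neither absorption rates nor enrolment delays. The defect in timing does not depend on them. It is worth correcting because the affected outcome is the one used to size the trial and the correction is cheap.

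**What to change.** 1. In Sections 2, 3, 6 and 11, define day 0 as randomisation in both arms, so that the scans fall 4 months and 1 year after randomisation and GOSE 1 year after randomisation. In Section 9, state randomisation as time zero for the time-to-absorption analysis.
2. In Section 4, state a maximum interval from index surgery to randomisation. Its length is for the sponsor to choose, but it should be shorter than the time to the first assessment.
3. Record time since index surgery as a baseline variable.

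The cost is protocol wording. Each patient's visits move later by that patient's enrolment delay, and a few late presenters may become ineligible. No visits or scans are added.

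### The protocol does not say how patients who enter with a tense lesion (PPS IV) count towards the tension part of the primary outcome, and Sections 6 and 9 can give different answers

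*Protocol*

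**What the plan says.** - **Entry (Protocol, Section 4).** The inclusion criterion is "Diagnosed fluctuation during clinical examination after the surgery, Pseudomeningocele Palpation Scale (PPS), II-IV". The top grade is defined as "IV Tense lesion; painful and/or erythematous; underlying structures are not palpable even with firm pressure". No exclusion criterion removes these patients: the one on urgent surgery covers only conditions unrelated to the pseudomeningocele.
- **Objective (Section 2).** "New onset of wound CSF leakage necessitating revision surgery". There is no tension component.
- **Primary outcome (Section 6).** "New onset of wound CSF leakage or tension pseudomeningocele necessitating revision surgery".
- **Primary analysis (Section 9).** "The proportion of patients requiring revision surgery for CSF leakage or tension pseudomeningocele at 4 months and 1 year" is compared between the arms by a chi-square test. The words *new onset* do not appear.
- **Assigned treatment.** Section 5 lists revision surgery among the interventional procedures and describes it as "Surgical intervention to drain the pseudomeningocele and ensure proper wound closure". Section 3 describes the same arm by lumbar drainage, puncture, fibrin glue or a combination, without revision surgery.
- **Use of PPS.** Randomisation is stratified by age and body mass index. Section 9 gives baseline health status, age and type of initial surgery as examples of confounders. PPS grade is in neither list.

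**The concern.** A state that patients may have at entry is also named as a component of the primary outcome, and the protocol does not say how the two relate. For a PPS IV entrant, *new onset* of tension has no defined meaning. The analysis section avoids the problem by dropping the qualifier, but it then defines a different event from Section 6.

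This decides who counts as a primary event, so it is more than a matter of style. Surgical teams and patients are unblinded, and no criterion is given for when revision is necessitated. If the counting rule is left open, it may be chosen once the results in PPS IV patients are known. With 30 patients per arm, reclassifying a few of them can matter.

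**Working it through.** **The plan's own figure.** The 60 patients in Section 8 are justified by absorption, not by the primary outcome, and no rates, effect size or dropout are given. The figure cannot be reproduced and does not bear on this point.

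**Reading the sections side by side.** Take a patient who is PPS IV at randomisation, and assume that tension pseudomeningocele means a lesion of the PPS IV type. The wording suggests this, but the protocol does not state it.

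| Course after entry | Section 2 | Section 6, *new onset* covers both terms | Section 6, *new onset* covers leak only | Section 9 |
|---|---|---|---|---|
| Stays tense, no revision needed | no event | no event | no event | no event |
| New leak, revised | event | event | event | event |
| Stays tense, later revised for tension | no event | no event | event | event |
| Revised for tension as the assigned Section 5 procedure | no event | no event | not settled | could be an event |

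The first two rows agree throughout. The conflict lies in the third row. The fourth adds a problem that arises only in the interventional arm, and only if Section 5 rather than Section 3 describes that arm.

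**How much could it matter?** The documents give no event rates and no grade IV share, so what follows is illustration only. Assumptions: event rates of 40% (conservative) and 10% (interventional), 30 per arm, two-sided alpha 0.05, and a grade IV share f of 10%, 20% or 30% (3, 6 or 9 patients per arm).

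Power = Φ[(|p1 − p2| − 1.96·SE0)/SE1], with SE0 = √(2·p̄(1 − p̄)/30), p̄ the mean of the two rates, and SE1 = √((p1(1 − p1) + p2(1 − p2))/30). For 40% versus 10% the power is 78%.

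- *Strict reading of Section 6.* Assume half of the grade IV patients' events would be tension events, and these are not counted. Both rates are multiplied by 1 − 0.5f, giving 38% v 9.5%, 36% v 9% and 34% v 8.5%. Power is 75%, 72% and 68%.
- *Section 9 wording with assigned revision counted.* Assume half of the interventional grade IV patients have revision as assigned treatment and each counts as an event. The interventional rate is 0.10 + f × 0.5 × 0.90 = 14.5%, 19% and 23.5%, against 40%. Power is 61%, 43% and 28%.

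The first reading removes events from both arms. The second adds events to the interventional arm only. Under these assumptions the choice of reading ranges from a small loss of power to a large distortion of the contrast.

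**The case against.** The other side has several good arguments.

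1. The outcome needs a lesion that necessitates revision surgery, and Section 9 counts patients who require it. A tense lesion at entry is not an event by itself. This stands: a reader might infer that PPS IV patients meet the endpoint on the day they enter, but the text rules that out.
2. A PPS IV entrant can still have a new leak that needs revision. This stands too. Such patients are not structural non-events. At most the tension component is closed to them, and only if *new onset* governs both terms.
3. Grade at entry is independent of arm by randomisation. If untreated tense lesions go on to need revision more often than treated ones, that is the treatment contrast and not bias. This is largely right. A reader might infer a calculable bias against the conservative arm, but that would require every conservative PPS IV patient, and no interventional one, to become an event through tension. Nothing in the protocol supports this, and the assigned-revision problem points the other way.
4. The covariates in Section 9 are given as examples, and the analysis plan, which is not at hand, may include PPS. This stands, so the absence of PPS is not an error in itself.
5. A reader might see a clash between erythema in grade IV and the exclusion "Known or suspected infection at the pseudomeningocele site at the time of recruitment". The two criteria apply together, and grade IV does not require erythema, so there is no contradiction.

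None of these arguments says whether revision for persisting tension in a PPS IV entrant is a primary event.

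**Conclusion.** The point holds as a conflict in the definition of the primary event. For a patient who is PPS IV at entry and later revised for persisting tension, Section 9 gives an event. Section 6 gives a non-event for that component if *new onset* covers both terms, and Section 2 has no tension component at all. The undefined term and the disagreement between Sections 3 and 5 on revision surgery widen the gap.

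The conclusion rests on two readings that the protocol suggests but does not state: that tension pseudomeningocele corresponds to PPS IV, and that *new onset* may apply to tension as well as to leakage. The size and direction of the effect are unknown, and the power figures above depend wholly on assumed rates and shares. Because the conflict concerns the primary event, it should be settled before any outcome data are seen.

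**What to change.** 1. Use one identical event definition in Sections 2, 6 and 9. Define tension pseudomeningocele relative to PPS, and state how patients who are PPS IV at randomisation count, by the same rule in both arms.
2. One workable rule is to count any revision surgery after randomisation for leak or tension that is not the assigned procedure, whatever the entry grade. A sensitivity analysis would leave out tension events in PPS IV entrants. Restricting these patients to the leak component in the main analysis is more debatable, because it would discard revisions for persisting tension that may be treatment failures.
3. Record PPS at randomisation, and pre-specify II-III versus IV as a covariate in an adjusted analysis of the primary outcome.
4. Reconcile the lists of interventional procedures in Sections 3 and 5, so that it is clear whether revision surgery can be assigned treatment. The entry range and clinical management remain for the sponsor to decide.

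The cost is changes of wording and one small extra analysis. PPS is already assessed for eligibility, so little or no new data collection is needed.

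### Eligibility admits patients who may already have a CSF leak or a tense lesion, the primary outcome asks for new onset, and the Section 9 analysis drops that qualifier

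*Protocol*

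**What the plan says.** All references are to the Protocol.

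- **Section 4, inclusion.** The population is "Patients aged 18-80 years who have developed a pseudomeningocele following elective intracranial surgery". The wound criterion is "Diagnosed fluctuation during clinical examination after the surgery, Pseudomeningocele Palpation Scale (PPS), II-IV". The top eligible grade is "IV Tense lesion; painful and/or erythematous; underlying structures are not palpable even with firm pressure". Nothing is said about a dry or closed wound.
- **Section 4, exclusion.** The only exclusion on the local state of the wound is infection. The only one on need for surgery reads "Patients with conditions that require urgent surgical intervention not related to pseudomeningocele management".
- **Section 2, primary objective.** "New onset of wound CSF leakage necessitating revision surgery".
- **Section 6, primary outcome.** "New onset of wound CSF leakage or tension pseudomeningocele necessitating revision surgery".
- **Section 9, primary analysis.** "The proportion of patients requiring revision surgery for CSF leakage or tension pseudomeningocele at 4 months and 1 year will be compared".
- **Section 5, conservative arm.** Patients have "no surgical procedures other than the application of skin sutures if required".

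**The concern.** An endpoint defined by new onset needs one of two things: a population free of the condition at entry, or a recorded baseline status that lets new cases be told from existing ones. Section 4 provides neither for leakage. For tension, it admits the tense grade by name. Section 9 then removes the only words that would have separated new from existing cases.

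At stake is what the primary comparison estimates. If patients with an existing leak or a tense lesion are enrolled and revised for it, the rate blends preventing a complication with treating one already there. Two people applying the protocol in good faith could also code the same patient differently on the primary outcome. With 30 patients per arm, one recoded patient moves an arm's rate by 1/30 = 3.3 percentage points. Stratification is by age and body mass index only, so baseline wound status is balanced between arms in expectation but not by design.

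**Working it through.** **Step 1. Does any criterion remove a leaking wound?** The inclusion criteria cover age, elective surgery, palpation grade, consent and no earlier cranial or spinal surgery. The exclusions cover emergency or trauma surgery, local infection, severe comorbidity and urgent surgery for unrelated conditions. None mentions leakage, and the last is limited in terms that leave a leak outside it.

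**Step 2. How would the same patient be counted?**

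| Status at entry, and reason for revision | Section 2 | Section 6 | Section 9 |
|---|---|---|---|
| Dry, not tense; a leak arises later | event | event | event |
| Leaking; revised for that leak | no event | no event through the leak component | event |
| Leaking; becomes tense later, revised for tension | not covered | event | event |
| Leaking; leak stops and recurs, revised | unclear, new onset undefined | unclear | event |
| Grade IV; revised for tension | not covered | depends on whether new onset also governs tension | event |

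Only the first row is counted alike in all three sections.

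**Step 3. The plan's own figure.** Section 8 gives 60 patients (30 per group), 80% power and alpha 0.05, for a difference in absorption. It states no rates, so 60 cannot be reproduced, and the point does not depend on it.

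**Step 4. Illustration of size.** Every rate here is an assumption. Let p be the event risk in patients not leaking at entry, f the share leaking at entry (the same in both arms) and q their risk of revision (also the same in both arms).

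- Limiting strict reading, in which baseline leakers never become events: arm rate = (1 − f)p.
- Section 9 as worded: arm rate = (1 − f)p + fq.
- Power = Φ{[|p1 − p2|√n − 1.96√(2p̄(1 − p̄))] / √(p1(1 − p1) + p2(1 − p2))}, with n = 30 per arm and p̄ the mean of the two rates.

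For 40% versus 10% and f = 10%, the strict rates are 0.9 × 0.40 = 0.36 and 0.9 × 0.10 = 0.09. Under Section 9 with q = 60% they are 0.36 + 0.06 = 0.42 and 0.09 + 0.06 = 0.15. The difference is 27 points either way, against 30 points with no baseline leakers.

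| Assumed risks | Power, f = 0 | f = 10%, strict | f = 10%, Section 9, q = 30% to 60% | f = 20%, strict | f = 20%, Section 9, q = 30% to 60% |
|---|---|---|---|---|---|
| 40% v 10% | 0.78 | 0.72 | 0.68 to 0.65 | 0.65 | 0.57 to 0.51 |
| 30% v 5% | 0.73 | 0.68 | 0.61 to 0.56 | 0.61 | 0.49 to 0.42 |
| 50% v 15% | 0.84 | 0.78 | 0.76 to 0.74 | 0.71 | 0.65 to 0.61 |

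The two readings differ by 60fq events: 60 × 0.10 × 0.30 = 1.8 to 60 × 0.10 × 0.60 = 3.6 at f = 10%, and 3.6 to 7.2 at f = 20%. Because q is equal in both arms, this shows dilution and ambiguity, not bias towards either arm.

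**The case against.** The Section 9 sentence stands under the primary outcome and can be read as shorthand for the Section 6 definition, with details left to a statistical analysis plan. That has some force for wording. It does not reach eligibility: an analysis plan can define an event, but it cannot change who was enrolled or recover a wound status never recorded before treatment.

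A reader might infer three stronger points, and the protocol supports none of them.

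- *That a patient leaking at entry can never reach the Section 6 outcome.* Section 6 is a composite, so tension pseudomeningocele remains open to that patient. Since new onset is undefined, a leak that stops and recurs may count as well. Only the leak already present is closed.
- *That the sutures allowed in the conservative arm show leaking wounds are expected at entry.* Section 5 does not say why or when they would be placed. Closing a defect that appears after randomisation fits equally well. The protocol is silent on enrolling leaking wounds.
- *That the comparison is biased against the conservative arm.* Under 1:1 randomisation, patients leaking at entry are balanced in expectation. If one arm then had fewer of them revised, that would be a treatment effect in a subgroup. Section 5 also lists revision surgery among the interventional options while Section 3 does not, so revision could be allocated treatment. Read literally, Section 9 might count it as an event, which could push the difference the other way. Those two passages need reconciling in their own right.

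**Conclusion.** The point holds as an inconsistency between eligibility, endpoint and analysis. Section 4 does not keep out leakage present at recruitment and admits tense lesions; Sections 2 and 6 ask for new onset of leakage; Section 9 does not. Followed as written, Section 9 can count a condition present at entry as a primary event.

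The overlap for tension is the better documented half, because grade IV is an explicit entry grade. It still assumes that a tense lesion on palpation can be the same condition as tension pseudomeningocele, which the protocol does not define.

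The size is unknown, since the protocol gives no baseline frequency. On the assumed rates above, 10% of entrants leaking at baseline costs about 0.06 to 0.17 in power and leaves 1.8 to 3.6 events among 60 patients open to two codings. What is shown is a mixed estimand and an ambiguous event, not bias in a known direction. It should be corrected, because baseline status cannot be reliably reconstructed once treatment has begun.

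**What to change.** Reconcile Sections 2, 4, 6 and 9 in one amendment.

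1. In Section 4, make CSF leakage through the wound at recruitment an exclusion. If the sponsor prefers to keep such patients, then at minimum record dry or leaking status at the palpation examination, before randomisation.
2. In Sections 2 and 6, define the primary event once, as leakage or tension that newly arises after randomisation and necessitates revision. State whether a leak that stops and returns counts.
3. State how patients who enter at grade IV count towards the tension component. A leak exclusion alone does not settle this.
4. Use that same definition in the Section 9 primary analysis.

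The cost is a few lines of text, one baseline item at an examination already done and, if the exclusion is adopted, a slightly smaller recruitment pool.
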